- PSA partial response is defined as a $\geq 50\%$ decline in PSA from Cycle 1 Day 1 (baseline) PSA value. This PSA decline must be confirmed to be sustained by a second PSA value obtained 3 or more weeks later.

- PSA progression date is defined as the date that a $\geq 25\%$ increase and an absolute increase of ≥ 2 ng/mL above the nadir is documented, which is confirmed by a second consecutive value obtained four or more weeks later.

Table 24 Radiological Criteria for Ascribing Disease Progression

[figure not shown]
Evidence of Progression	Confirmation	Action
Bone Disease Appearance of two or more new bone lesions on bone scan	
≥ 2 new lesions at the first scheduled reassessment ≤ 13 weeks from Cycle 1 Day 1 compared with baseline; must be confirmed by a second scan performed 6 or more weeks later.
 
Confirmatory scans should show an additional 2 new lesions compared to the first post treatment scan (i.e., a total of ≥ 4 new lesions compared with the baseline bone scan).
	Investigators are highly encouraged to maintain the patient's treatment with study medication unless progression is confirmed.
Appearance of two or more new bone lesions on bone scan	
≥ 2 new lesions at the first scheduled reassessment > 13 weeks from Cycle 1 Day 1 compared with baseline; must be confirmed by a second scan performed 6 or more weeks later.
 
Confirmatory scans should confirm the presence of the 2 new lesions compared the baseline scan. (i.e., a total of ≥ 2 new lesions compared with the baseline bone scan).
	Investigators are highly encouraged to maintain the patient's treatment with study medication unless progression is confirmed.
Soft Tissue Disease as defined by RECIST on CT/MRI	Progression at any scheduled reassessment should be confirmed.	Investigators are highly encouraged to maintain the patient's treatment with study medication unless radiological progression is confirmed.

[figure not shown]

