The non-GLP single dose PK study (Study 20133857 or HPN424PK-01) and a GLP-compliant toxicity study (Study 2012494 or HPN424TOX-01) as described in [Section 1.5](#), revealed a serum terminal half-life of approximately 3 days for HPN424 in cynomolgus monkeys. These findings support an initial dosing regimen of once weekly in humans.

3.3 *Study Duration and Dates*

Patient participation includes Screening (28 days), Treatment (ongoing in 21-day cycles), End of Treatment visit (within 7 days after the last dose of HPN424), and Safety Follow-up (SFU; 28 days [+ 7 days] after the last dose of HPN424), after which patients will enter long term follow-up (LTFU) for survival. Patients may continue weekly HPN424 treatment as long as they are receiving clinical benefit (as determined by the Principal Investigator and upon consultation with the Medical Monitor).

For purposes of estimating study duration, patients are expected to remain on treatment for approximately 28 weeks, making total study duration for each patient approximately 32 weeks through the SFU, or 18-24 months total including LTFU for survival. Given that patient recruitment is expected to occur over approximately 36 months, the study as a whole is expected to last approximately 48 months until the last patient completes the SFU.

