- ⁱ Chemistry: albumin (ALB), alkaline phosphatase (ALK-P), bone specific alkaline phosphatase (BAP), alanine aminotransferase (ALT; SGPT), amylase, aspartate aminotransferase (AST; SGOT), blood urea nitrogen (BUN), calcium (Ca), carbon dioxide (CO₂), chloride (Cl), creatinine, globulin, glucose, lactate dehydrogenase (LDH), lipase, magnesium, phosphorus, potassium (K), sodium (Na), total bilirubin, direct bilirubin, total protein, uric acid. C1D1 samples to be collected within 72 hours prior to dose. C1D8+ samples to be collected within 24 hours prior to dose. Additional ALK-P, ALT, AST, and total bilirubin samples to be collected at C1D1, C1D8, and C1D15—within 15 minutes after EOI and 5(± 1 h) after EOI.
- ^j Coagulation: prothrombin time/international normalized ratio (PT/INR), activated partial thromboplastin time (PTT). C1D1 samples to be collected within 72 hours prior to dose. C2+ Day 1 samples to be collected within 24 hours prior to dose.
- ^k Urinalysis: appearance, bilirubin, color, glucose, ketones, nitrite, occult blood, pH, protein, specific gravity, urobilinogen. C1D1 samples to be collected within 72 hours prior to dose; all subsequent Day 1 samples to be collected within 24 hours prior to dose.
- ^l Testosterone: tested via local laboratories
- ^m Pre-study tissue specimens are optional for all patients; if archival specimens meeting the requirements in the Laboratory Manual are not available, a fresh biopsy specimen may be collected prior to the start of study treatment.
- ⁿ The Investigator is to perform disease assessments with supporting blood and imaging evaluations and when clinically indicated, including at Early Termination if patient withdraws from study due to disease progression.
- ^o PSA: Baseline (on or within 14 days prior to Cycle 1 Day 1), every 9 weeks (e.g., Day 1 of Cycles 4, 7, 10, 13, etc.), and at EOT visit if not collected in the prior 9 weeks.
- ^p Imaging Tumor assessments are fixed relative to C1D1, irrespective of missed or delayed study treatments.
- ^q Bone scan: ^{99m}Tc-methylene diphosphonate radionuclide bone scintigraphy every 9 weeks (± 7 days) (e.g., Day 1 of Cycles 4, 7, 10, 13, etc.). Changes in lesions considered metastatic on bone scintigraphy should be followed and assessed serially using a bone scan assessment form [Appendix 7](#).

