- ^r CT/MRI imaging may include chest, abdomen, and pelvis CT or MRI scans (the same method should be used throughout the study). Brain scans will be performed at baseline if disease is suspected and on study as appropriate to follow disease. CT or MRI scans to be done every 9 weeks (± 7 days) (e.g., Day 1 of Cycles 4, 7, 10, 13, etc.). Tumor assessments should be repeated at the EOT visit if more than 9 weeks have passed since the last evaluation. Patients should have confirmatory scans for response or progression and should remain on treatment if they are receiving clinical benefit (as determined by the Principal Investigator and upon consultation with the Medical Monitor).
- ^s PSMA PET to be performed at selected sites only.
- ^t HPN424 IV will be administered via 1-hour infusion. HPN424 will be administered once weekly (-2 days/+1 day) with a minimum of 4 non-dose days between 2 consecutive doses. Doses are to be calculated based on the patient's baseline (Screening) body weight, not adjusted each cycle for weight at Day 1 of each cycle. Please refer to [Section 5.1.4 Hospitalization and Monitoring](#) for additional instruction on requirements for post-dose monitoring.
- ^u Adverse events (including serious AEs [SAEs]) recorded from signing of informed consent form through the SFU (≥ 28 days [+7 days] after last dose of HPN424).

- ^v C-reactive protein (CRP): at C1D1—predose (-72 h), 5 h (\pm 1 h) after end of infusion (EOI), C1D2—24 h (\pm 1 h) after EOI; C1D8—predose (-24 h); once per cycle (predose [- 24 h] starting with Cycle 2), and when signs of cytokine release syndrome (CRS) are observed.
- ^w 12-Lead ECG: Patients should be resting in a supine or sitting position for \geq 10 minutes prior to electrocardiogram (ECG) collection. Obtain 1 ECG pre-dose at each of the following timepoints: Screening; D1 of each cycle; EOT visit. If cardiac abnormalities are detected or suspected, two additional ECGs must be performed to further evaluate and each reading should be obtained at least 3 minutes apart.
- ^x Pulse oximetry: Within 1 hour prior to each dose.

Table 16 Intravenous Fixed Dosing Regimen: Research Specimen Collection

Cycle	Study Day	Cytokines ^a	Immuno-phenotyping	CTC	PK ^b	Anti-Drug Antibodies
Cycle 1	C1D1-Pre dose	X	X	X	X	X
	C1D1-EOI				X	
	C1D1-2 h Post EOI				X	
	C1D1-5 h Post EOI	X	X		X	
	C1D2	X	X		X	
	C1D3	X	X		X	
	C1D5				X	
	C1D8-Pre dose	X			X	
	C1D8-EOI				X	
	C1D8-5 h Post EOI	X			X	
	C1D15-Pre dose	X		X	X	X
	C1D15-EOI				X	

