- If CR determination depends on a residual lesion that decreased in size but did not disappear completely, it is recommended the residual lesion be investigated with biopsy or fine needle aspirate. If no disease is identified, objective status is CR.
- If progression determination depends on a lesion with an increase possibly due to necrosis, the lesion may be investigated with biopsy or fine needle aspirate to clarify status.

Subjective Progression

Patients requiring discontinuation of treatment without objective evidence of disease progression should not be reported as progressive disease (PD) on tumor assessment CRFs. This should be indicated on the CRF as discontinuation of treatment due to Global Deterioration of Health Status.

Every effort should be made to document objective progression even after discontinuation of treatment.

ASSESSMENT OF RADIOGRAPHIC RESPONSE AND PROGRESSION IN PATIENTS WITH METASTATIC CRPC

Radiographic imaging for patients with CRPC is categorized as soft tissue or bone. Soft tissue imaging may include CT scans of the chest, abdomen and pelvis or MRIs of the abdomen and pelvis. Bone imaging must be whole body radionuclide bone scan.

The Investigator will assess response of soft tissue disease as described above. However, bone disease is not to be considered as nontarget lesions.

Bone disease will be assessed for progressive disease only by PCWG3. The documentation required for the determination of radiographic progression is shown in [Table 20](#).

Table 20 Criteria for Evidence of Radiographic Progression

Date Progression Detected ^a	Criteria for Progression	Criteria to Confirm Progression	Criteria to Document Disease Progression on Confirmatory Scan
Week 9	Bone lesions : 2 or more new lesions compared to screening bone scan by PCWG3	Timing: At least 9 weeks after progression identified or at Week 18 visit ^b	2 or more new bone lesions on bone scan compared to Week 9 scan
	Soft tissue lesions : Progressive disease on CT or MRI by RECIST v1.1	Confirmatory scan required for soft tissue disease progression	No confirmatory scan required for soft tissue disease progression
Week 18 or later	Bone lesions: 2 or more new lesions on bone scan compared to Week 9 bone scan	Timing: At least 9 weeks after progression identified or at next imaging timepoint ^b	Persistent or increase in number of bone lesions on bone scan compared to prior scan ^c

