	Soft tissue lesions: Progressive disease on CT or MRI by RECIST v1.1	Confirmatory scan required for soft tissue disease progression	Confirmatory scan required for soft tissue disease progression

Abbreviations: CR=complete response, PD=progressive disease, PR=partial response, SD=stable disease, NE=nonevaluable.

- a. Progression detected by bone scan at an unscheduled visit either before Week 9 or between scheduled visits will require a confirmatory scan at least 9 weeks later and should follow confirmation criteria outlined in the table for the next scheduled scan.
- b. Confirmation must occur at the next available scan.
- c. For confirmation, at least 2 of the lesions first identified as new must be present at the next available scan (confirmation scan).

Disease progression in bone must be confirmed at least 9 weeks later, as per PCWG3. See [Table 21](#) below for the timing of confirmatory imaging requirements.

Table 21 Confirmatory Imaging Requirements for Patients with CRPC Based on RECIST v1.1 and PCWG3

Disease Site	Response	Progression ^a
Soft tissue	Must be confirmed at least 9 weeks later	Confirmation required
Bone	Not applicable	Must be confirmed at least 9 weeks later
a. To inform permanent treatment discontinuation		

Radiographic progression-free survival (PFS) is defined as the time from enrollment to documentation of radiographic progression in soft tissue by Investigator's assessment according to RECIST v1.1 ([Table 22](#), [Table 23](#)), in bone by Investigator's assessment according to PCWG3, or death, whichever occurs first.

Table 22 Objective Response Status at Each Evaluation

Target Lesions	Nontarget Disease	New Lesions	Objective Status
CR	CR	No	CR
CR	Non-CR/non-PD	No	PR
CR	Indeterminate or Missing	No	PR
PR	Non-CR/non-PD, indeterminate, or missing	No	PR
SD	Non-CR/non-PD, indeterminate, or missing	No	Stable
Indeterminate or missing	Non-PD	No	Indeterminate
PD	Any	Yes or No, including bone determination	PD
Any	PD	Yes or No	PD
Any	Any	Yes	PD

Abbreviations: CR=complete response, PD=progressive disease, PR=partial response

If there is a protocol deviation and a patient has been enrolled with only nontarget disease, [Table 23](#) will be used.

Table 23 Objective Response Status at Each Evaluation for Patients with Nontarget Disease Only

Nontarget Disease	New Lesions	Objective Status
CR	No	CR
Non-CR/Non-PD	No	Non-CR/Non-PD
Indeterminate	No	Indeterminate
Unequivocal progression	Yes or No	PD
Any	Yes	PD

[figure not shown]

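### Table 21's 9-week minimum for confirming a soft-tissue response equals the scan interval and ignores the ±7-day window, so two on-schedule scans that both show response can fail to confirm it

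*Protocol*

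**What the plan says.** Protocol Appendix 6, Table 21, soft-tissue row, response column: a response "must be confirmed at least 9 weeks later". The cell has no window and no visit-based alternative.

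Protocol Appendix 1, footnote r (same timing in Appendices 2 to 4): "CT or MRI scans to be done every 9 weeks", each with a ±7-day window. Footnote p: "Imaging Tumor assessments are fixed relative to C1D1, irrespective of missed or delayed study treatments". Footnote r adds: "Patients should have confirmatory scans for response or progression". It gives no separate timing for them.

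Table 20 treats bone progression differently. At Week 9 the confirmatory scan is due on these terms: "Timing: At least 9 weeks after progression identified or at Week 18 visit". From Week 18 on, the alternative is the next imaging timepoint.

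Protocol Section 10.8 bases efficacy on radiographic response under PCWG3 and points to Appendix 6. It defines ORR as CR or PR and does not mention confirmation. SAP Section 9.1.1 states that best overall response needs no confirmation. SAP Sections 3 and 5.4 record that Part 2 was not initiated and that efficacy data appear only in by-patient listings.

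**The concern.** The minimum confirmation interval is exactly the nominal scan interval, yet each scan may move 7 days either way around its own calendar date. A site can keep both scans on schedule, see PR on both, and still have a pair 62 days apart that Table 21 does not accept. Whether a patient counts as a confirmed responder at the first attempt then depends partly on appointment dates.

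The stake is the protocol's Dose Expansion primary endpoint, ORR, and DOR, which is measured only in responders. Responses that end before a second confirmation attempt could be left out. That would lower a confirmed ORR and make the responder group behind DOR smaller and selective.

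**Working it through.** **Inputs**
- Minimum gap to confirm: 9 weeks = 63 days (Table 21).
- Scan interval and window: 63 days, each scan at an offset of −7 to +7 days (Appendix 1, footnote r).
- Anchor: C1D1, not the previous scan (footnote p), so the two offsets act separately on the gap.
- Expected time on treatment (Section 3.3): "patients are expected to remain on treatment for approximately 28 weeks".

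**The plan's own figures.** The documents give none for the share of scan pairs that are too close. The nearest are for the two-stage ORR design in Protocol Section 10.2 (continue if at least 1 of 14 respond, succeed if at least 2 of 20). They reproduce:
- Early termination at 1%: 0.99^14 = 0.869.
- Expected size: 14 + 6 × (1 − 0.869) = 14.8.
- Type 1 error: 1 − 0.99^14 − 14 × 0.01 × 0.99^19 = 0.016.
- Power at 15%: 1 − 0.85^14 − 14 × 0.15 × 0.85^19 = 0.801, so type 2 error is 0.199.

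**Range of gaps.** Gap = 63 + (second offset − first offset). Minimum 63 − 14 = 49 days; maximum 63 + 14 = 77 days.

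**Share under 63 days.** There are 15 × 15 = 225 permitted offset pairs. The gap is under 63 when the second offset is smaller than the first: 14 + 13 + … + 1 = 105 pairs. Another 15 pairs are exactly 63 days apart and 105 are longer.

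If the two offsets are independent with the same distribution, the share is (1 − P(same offset)) / 2, which cannot exceed 50%. The documents do not give the distribution, so these are assumptions:

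| Scan-date scatter | P(same offset) | Share under 63 days |
|---|---|---|
| Uniform over ±7 days | 1/15 = 0.067 | 46.7% |
| Normal, SD 3 days | 0.096 | 45.2% |
| Normal, SD 2 days | 0.141 | 42.9% |
| Half on the nominal day, rest uniform | 0.268 | 36.6% |
| Normal, SD 1 day | 0.282 | 35.9% |
| 80% on the nominal day, rest uniform | 0.643 | 17.9% |

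**The next attempt.** The scan after that is 126 ± 14 days from the first, i.e. 112 to 140 days, and always satisfies the rule. For a response first seen at Week 9 it falls at Week 27, just inside the expected 28 weeks on treatment. For a response first seen at Week 18 it falls at Week 36, after that expected time.

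**Other minimum intervals.** With a floor of 56 days, 7 + 6 + … + 1 = 28 of 225 pairs (12.4%) would still fail. With 49 days, none would.

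**The case against.** The strongest reply is that both rules can always be met together. If the first scan is at offset a, any second scan from offset a to +7 is in window and at least 63 days later. Even a first scan at +7 leaves one valid day. This is correct, so the conflict is avoidable. But the protocol nowhere tells sites to book the second scan no earlier in its window than the first, and after a late first scan few days remain.

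Three stronger readings are tempting and go too far.

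- *Nearly half of on-schedule pairs would fail.* That treats 105 of 225 permitted pairs as an expected frequency. It needs independent, widely scattered scan dates, which the documents do not establish.
- *The rule rejects valid responses.* It is a floor, so a later scan can still confirm. Table 20's footnote requiring confirmation at the next available scan concerns progression, not response. Section 6.20 also continues imaging after treatment stops. That protection is uncertain, because Section 6.18 runs disease assessments only until treatment discontinuation and before new therapy, and Sections 6.24 and 8.3 waive end-of-treatment imaging done within 9 weeks.
- *The design loses power.* If every too-close responder were never confirmed, 15% × (1 − 0.467) = 8.0%, and the chance of passing the 14 + 6 rule would fall from 0.80 to 0.46. The documents give no fraction never confirmed, and Section 10.2 does not say whether 15% is a confirmed or unconfirmed rate. This is an extreme case, not an estimate of loss.

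The SAP's waiver and the closure before Part 2 also stand as limits on impact. They do not settle which rule governs: SAP Section 11 says no protocol-specified analysis was changed, so the waiver is not declared as replacing Table 21.

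**Conclusion.** The point holds as a drafting fault in a response rule. As written, a fully compliant pair of scans both showing PR can fail Table 21, and the response cell lacks the alternative that Table 20 gives bone progression. The share of first attempts affected runs from about 18% to 47% across the scatter assumptions tried, and would be zero if sites timed the second scan deliberately.

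The usual effect is delay. A response is lost only if the patient progresses or stops imaging before the later scan. A protocol-defined confirmed ORR could therefore be biased downward, and DOR would rest on fewer and selected responders; neither amount can be worked out from the documents. If SAP Section 9.1.1 governs, the final listings are not affected. If Table 21 governs, responder status in those listings could depend on scan dates.

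**What to change.** Change the soft-tissue response cell of Table 21 to: *must be confirmed at the next or a later scheduled scan (9 weeks, within the ±7-day visit window, i.e. at least 7 weeks later)*. Seven weeks is 9 weeks less one week for each scan's window, so no compliant pair fails. Allowing a later scan keeps confirmation possible after a missed or indeterminate one.

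Reconcile this with SAP Section 9.1.1 by stating which rule governs response and DOR. As the study has closed, the synoptic report should at least say which rule the listings use.

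The cost is one table cell and one sentence, with no added scans. The downside is that some responses are confirmed after 7 to 9 weeks instead of at least 9.

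For bone progression, the confirmation timing differs between Table 20 (at least 9 weeks, or the Week 18 visit or next imaging timepoint), Table 21 and the sentence above it (at least 9 weeks), and Table 24 (6 or more weeks). Table 21 marks its progression column as informing permanent treatment discontinuation, so these passages must be reconciled by the sponsor; no rule is proposed here.

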4.2 Inclusion Criteria

Each patient must meet the following criteria to be enrolled in this study:

1. Male patients ≥ 18 years of age at the time of signing informed consent
2. Histologically or cytologically confirmed adenocarcinoma of the prostate
3. Progressive metastatic castrate-resistant prostate cancer (mCRPC):
 - a. Serum testosterone levels less than 50 ng/dL (or ≤ 0.50 ng/mL or 1.73 nmol/L) within 28 days prior to start of study drug
 - b. Radiographic evidence of metastatic disease
 - c. Disease progression on the prior systemic regimen, per Prostate Cancer Clinical Trials Working Group 3 (PCWG3) criteria ([Scher, 2016](#)) described in protocol [Appendix 6](#):
 - i. A sequence of at least 2 rising PSA values measured at a minimum of 1 week apart with a 2 ng/mL minimum starting value, or
 - ii. Appearance of two or more new lesions on bone scans, or
 - iii. Progressive visceral disease, or
 - iv. Progressive nodal disease; previously normal (<1.0 cm) lymph nodes must have grown by ≥ 5 mm in the short axis from baseline or nadir and be ≥ 1.0 cm in the short axis to be considered to have progressed
4. Must have received at least 2 prior systemic therapies approved for mCRPC
5. Ongoing androgen depletion therapy with a gonadotropin releasing hormone analog or inhibitor, or orchectomy (surgical or medical castration)
6. For patients previously treated with first generation anti-androgens, discontinuation must have occurred ≥ 4 weeks (for flutamide or nilutamide) or ≥ 6 weeks (for bicalutamide) prior to start of study drug, with no evidence of an anti-androgen withdrawal response (i.e., no decline in serum PSA)
7. For patients previously treated with a second-generation anti-androgen (e.g., enzalutamide or equivalent) or with abiraterone acetate, discontinuation must have occurred 2 weeks or 5 half-lives prior to start of study drug

8. For patients previously treated with systemic chemotherapy, targeted therapy, immunotherapy, or treatment with an investigational anticancer agent, discontinuation must have occurred ≥ 2 weeks, or at least 4 half-lives (up to 4 weeks), whichever is longer, prior to start of study drug.
9. Eastern Cooperative Oncology Group (ECOG) performance status of 0 or 1
10. Adequate bone marrow function, including:
 - a. Absolute neutrophil count (ANC) $\geq 1500/\text{mm}^3$ or $\geq 1.5 \times 10^9/\text{L}$
 - b. Platelets $\geq 100,000/\text{mm}^3$ or $\geq 100 \times 10^9/\text{L}$

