6.18 Disease Assessments

Patients will be assessed for disease status by the Investigator, according to the PCWG3 recommendations ([Scher, 2016](#)) ([Appendix 6](#)). The Investigator will record Biochemical Response (based on PSA) and Radiographic Response (based on bone scans and, for those with soft tissue disease, CT or MRI results) at timepoints as outlined in the appropriate Schedule of Assessments and at other times if clinically indicated.

Key disease assessments (PSA, bone scans and CT/MRI) are to be performed per the appropriate Schedule of Assessments irrespective of whether treatment is delayed or missed. In other words, the schedule for these items is calendar-based and fixed relative to C1D1.

Note: in patients who show evidence of clinical benefit, PCWG3 advises continuing therapy until the patient is no longer clinically benefitting (NLCB), not strictly at the first sign of

disease progression. PCWG3 draws the distinction between documenting progression for consistency of reporting (e.g., recording the date of documented progression in a site of disease such as a lymph node that is unlikely to adversely affect prognosis) versus the decision to stop therapy. In this study, patients may continue weekly HPN424 treatment as long as they are receiving clinical benefit (as determined by the Principal Investigator and upon consultation with the Medical Monitor).

Disease assessments are to continue (unless the patient withdraws consent or is lost to follow-up), until discontinuation of study treatment and prior to initiation of new anticancer therapy.

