10.2 Determination of Sample Size

Up to 150 patients with mCRPC may be enrolled. The number of cohorts and patients will depend on data observed during Dose Escalation.

Dose Escalation may include up to 130 patients, depending on the dose at which the MTD and RP2D(s) are determined. The sample size and design of the Dose Escalation portion of the study are consistent with those in other oncology studies used to determine MTD. The traditional 3 + 3 dose escalation scheme employs the standard NCI definition of MTD (highest dose associated with DLT in <33.3% of patients) for each arm.

Dose Expansion will include up to 20 evaluable patients using a Simon 2-stage design to assess preliminary clinical efficacy of HPN424 at the RP2D(s). Power calculations based on a Simon 2-stage minimax design ([Simon, 1989](#)) test the null hypothesis that overall response rate (ORR) ≤ 0.01 versus the alternative hypothesis that ORR ≥ 0.15 , with a Type 1 error rate of 0.05 and power of 80%. This design would allow identification of a target response rate of 15% or better in a population of patients who have failed standard available therapy and would not be expected to have any responders.

A sample size of 14 evaluable patients will be enrolled in the first stage. If the total number responding (defined as partial response [PR] or complete response [CR] is ≥ 1 , an additional 6 evaluable patients will be enrolled in the second stage for a total of 20 evaluable patients. If the total number responding is ≤ 1 , the effectiveness of treatment based on ORR will be rejected. If treatment is actually not effective and ORR 0.01, then the expected sample size is 14.8 evaluable patients with a 0.869 probability of early termination and there is a 0.016 probability of incorrectly concluding the treatment is effective (the target for this Type 1 error rate was 0.05 or less). If the treatment is actually effective, there is a 0.199 probability of incorrectly concluding it is not effective (the target for this Type 2 error rate was 0.20 or less).

While the intention is to study a single RP2D, additional expansion cohorts of up to 20 patients per expansion cohort may be added at the recommendation of the CRC. If the CRC recommends multiple RP2Ds, each will be evaluated with independent Simon 2-stage designs of up to 20 evaluable patients per RP2D.

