10.3 Analysis Populations

Safety analyses will be based on the Safety Population, defined as all patients who have received any amount of HPN424.

Efficacy analyses will be performed based on the Efficacy Evaluable Population, defined as all patients who have received any amount of HPN424 at the assigned RP2D and who have any evaluable post baseline disease assessment. Patients who withdraw from study treatment due to clinical progression or death without post baseline assessments will be considered non-responders.

PK analyses will be based on the PK Evaluable Population, defined as all patients who have received any amount of HPN424 and who have any evaluable post baseline PK assessment.

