8.3 Protocol Deviations

Protocol deviations will be identified by the Investigator and/or Harpoon as major and minor and classified by type before the database is locked. The patient incidence of major protocol deviations will be summarized for Safety Population overall and by the following major categories:

- inclusion and/or exclusion criteria (those who entered the study even though they did not satisfy the entry criteria)
- withdrawal criteria (those who developed withdrawal criteria during the study but were not withdrawn)
- study drug or dosing criteria not met (those who received the wrong treatment or incorrect dose or dosing error [modify as appropriate if only doses outside certain limits are considered major treatment deviations])
- concomitant medication/therapy (those who received a prohibited concomitant treatment)
- informed consent (those from whom informed consent was not properly obtained)
- deviations attributed to COVID-19

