9 EFFICACY

All efficacy data will be reported only in by-patient data listings.

Best overall response (BOR), progression-free survival (PFS), overall survival (OS), duration of response (DOR), and change from baseline in PSA are all secondary endpoints for Part 2 Dose Escalation. Duration of disease control (DODC) is an additional exploratory endpoint for this study.

All efficacy endpoints derived from tumor imaging and response assessments are determined by the investigator using Prostate Cancer Working Group Criteria 3 (PCWG3). Evaluations of overall response are identified as complete response (CR), partial response (PR), stable disease (SD), progressive disease (PD), or not evaluable (NE).

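### Do patients without target lesions need new rules in Protocol Appendix 6 and the SAP's efficacy sections?

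*Protocol*

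**What the plan says.** **Entry.** Protocol 4.2, criterion 3b, asks for "Radiographic evidence of metastatic disease". Progression may be shown by PSA, bone scan, visceral disease or nodal disease. No criterion requires a target or measurable lesion, and Appendix 6 confirms that PSA or bone-scan progression is enough. Section 6.18 bases radiographic response on bone scans and, "for those with soft tissue disease, CT or MRI results".

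**Response tables.** Appendix 6 introduces Table 23 with "If there is a protocol deviation and a patient has been enrolled with only nontarget disease". Table 23 scores such patients CR, Non-CR/Non-PD, Indeterminate or PD. Bone lesions are kept out of that table: "However, bone disease is not to be considered as nontarget lesions". Bone is assessed for progression only, and Table 21 gives no response requirement for it.

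**SAP.** Section 9 uses five categories (CR, PR, SD, PD, NE). Section 9.1.6 counts CR, PR and SD as disease control. Section 9.1.2 censors PFS at the last tumor assessment that could be evaluated and refers to 13.2 for detail. Three of the four censored rows in 13.2 use instead the last radiological assessment of the measured lesions. Section 8.3 describes entry deviations as "those who entered the study even though they did not satisfy the entry criteria".

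**Populations and design.** The Efficacy Evaluable Population in Protocol 10.3 takes treated patients "who have any evaluable post baseline disease assessment", with no target-lesion condition. Protocol 10.2 aims at "a target response rate of 15% or better in a population of patients who have failed standard available therapy".

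**The concern.** Bone-predominant disease is common in this setting (Protocol 1.2 puts bone metastases at about 90% of CRPC patients), so patients with no target lesion are to be expected. The plan admits them in one place and calls them deviations in another. Once enrolled, a patient whose nontarget disease persists without progressing has a protocol status that the SAP does not recognise. A bone-only patient fits neither response table well. SAP 13.2, read literally, gives neither of them a censoring date.

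Three things could be at stake. The count of major entry deviations (SAP Table 14.1.3) could depend on which text is followed. Two identical patients could be listed differently, one as SD with a duration of disease control and the other as NE without one. If Dose Expansion had run, patients who could not be scored as responders would have sat in the ORR denominator.

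**Working it through.** **1. Design arithmetic (Protocol 10.2).** Inputs: 14 patients in stage 1, stop at 0 responses, 20 in total, drug rejected at 1 or fewer responses, null ORR 0.01, alternative 0.15.

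- Probability of early termination = (1 − p)^14. At p = 0.01 this is 0.99^14 = 0.8687.
- Expected sample size = 14 + 6 × (1 − 0.8687) = 14.79.
- Probability of success = 1 − (1 − p)^14 − [14p(1 − p)^13] × (1 − p)^6.
- At p = 0.01: 1 − 0.8687 − 0.1229 × 0.9415 = 0.0156.
- At p = 0.15: 1 − 0.1028 − 0.2539 × 0.3771 = 0.8015, so the type 2 error is 0.1985.

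The plan states 0.869, 14.8, 0.016 and 0.199. All reproduce.

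The 15% is most naturally read as the rate in the set defined in 10.3, and then power is unchanged. If it were meant only for patients with target lesions, and a share f of the set could not respond, the effective rate would be 0.15 × (1 − f). Power would be 0.6849 at f = 0.2 and 0.4256 at f = 0.5. These shares are assumptions, because the documents give none. The figures also overstate the loss, since Table 23 still allows a CR in nontarget-only patients. In any case Part 2 was not initiated (SAP 3 and 5.4).

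**2. Deviation count.** The Appendix 6 sentence is conditional and only chooses a scoring table; it adds no entry criterion. SAP 8.3 requires that an entry criterion was not met, and 4.2 contains none on target disease. Only major deviations, as classified by the investigator or sponsor before database lock, are summarized. With an assumed 5–20% nontarget-only share of the 130-patient cap, the arithmetic is 0.05 × 130 = 6.5 to 0.20 × 130 = 26. That difference appears only if every such patient is recorded as a major breach of a criterion that does not exist.

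**3. Response category.** Setting Table 23 against SAP 9:

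| Table 23 | SAP 9 |
|---|---|
| CR | CR |
| PD | PD |
| Indeterminate | NE (plausible reading) |
| Non-CR/Non-PD | not stated |

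Only the last row is open. Example on the 9-weekly calendar: Week 9 is Day 64 (9 × 7 + 1) and Week 27 is Day 190 (27 × 7 + 1). A patient who is Non-CR/Non-PD at Week 9 and has PD at Week 27 has a duration of disease control of 190 − 64 = 126 days if coded SD (127 with the SAP 7.2 day-count convention), and none if coded NE.

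**4. PFS dates.** Section 9.1.2 needs no target lesion: a bone-only patient without progression through Week 27 is censored at Day 190. Progression by new lesions, which is how bone progression is defined, and death are both dated in 13.2 without target measurements. The Day 1 row is for patients with no baseline tumor assessment. It does not apply here, because Protocol 6.20 requires bone scans and CT/MRI at screening. One case has no explicit row: nontarget progression without a new lesion. Section 9.1.2 runs PFS to the first documented progression, so the date of the scan that documents it is the evident choice.

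**5. Where the outputs go.** SAP 4.4 strikes PFS, DOR and OS from the endpoints addressed, and 4.2 strikes anti-tumor activity. SAP 3, 5.4 and 9 confine efficacy to by-patient listings. Target, nontarget, new-lesion, bone-scan and overall-assessment data are each listed separately (16.2.6.3 to 16.2.6.7), so a reader can see what lies behind any derived value.

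**The case for a change.** The best argument for a change is that the SAP says its purpose is to fix methods in advance, and here it leaves a coding choice to be made after the data are seen. Mapping Non-CR/Non-PD to SD is not automatic, because Appendix 6 defines stable disease under target disease and requires all target lesions to be assessed. Section 9.1.2 itself refers the reader to 13.2 for the detailed rules, so the two do conflict. The remedy would be a few sentences, with no extra patients, visits or data.

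The inconsistencies stand as described; their consequence does not follow. No derived efficacy value is tabulated, compared or tested. Whether Non-CR/Non-PD is shown with SD or on its own is a matter of convention, and either is acceptable if footnoted. Extending it to bone-only patients would go further than Appendix 6, which assesses bone for progression only. SAP 11 already provides for departures from the plan to be described in the study report, where such a choice can be recorded.

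**Conclusion.** No change is called for. The deviation wording before Table 23 is a clerical slip against 4.2. The missing mapping and the wording of 13.2 are gaps that an analyst would fill sensibly from 9.1.2 and the investigator's recorded assessment.

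The effect is confined to how some non-progressing patients, and any with nontarget progression but no new lesion, appear in by-patient efficacy listings. No summary table, test or dose decision depends on it. How many patients that is cannot be said: an assumed 20–50% of the 130 cap without target lesions would be 26–65 patients (0.20 × 130, 0.50 × 130), but that overstates the rows affected, since new-lesion progression and death are already dated.

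This conclusion rests on the SAP's statements that Part 2 was not initiated and that efficacy data will only be listed. Had Dose Expansion gone ahead with ORR as its primary endpoint, the meaning of the 15% target and the scoring of bone-only patients would have needed settling beforehand.
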